-Number of episodes of neurological deterioration in both groups of patients during the 12 days of treatment.

- Symptoms associated with TBI in both groups of patients during the 12 days of treatment.
- Volume of pericontusional edema before and after 12 days of treatment in both groups of patients.
- Presence of adverse events between the two groups during the 12 days of treatment.
- Neuropsychological tests between the two groups of patients one month and 6 months after the TBI.

Estimated event rate

In our previous studies we have described that among TBI patients with brain contusions not treated with dexamethasone, the proportion of patients with good recovery (GOSE 7 and 8) was 50%.

Sample size and treatment effect size that should be detectable

Since the data available in this type of patients with this treatment is scarce and inconclusive, we will perform a randomized, triple-blind, placebo controlled trial with an interim futility analysis (interim analysis). The primary endpoint for the DEXCON TBI trial is the good recovery (GOSE 7-8) one month after the TBI.

A study with 600 patients would have about 80% power (two sided alpha=5%) to detect a 12% absolute increased (from 50% to 62%) in good recovery (GOSE 7-8). It includes an inflation of 10% due to non-adherence (withdrawal of consent, loss to follow-up, cross-over or change of treatment).

Recruitment of collaborating investigators

The trial will recruit hospitals from Spain. Suitable collaborating hospitals and investigators will be assessed in terms of the trauma service that they provide and their ability to conduct the trial.

Before the trial can begin at any site, the local Principal Investigator must agree to adhere to Good Clinical Practice Guidelines and all relevant national regulations. In addition, all relevant regulatory and ethics approvals should be in place before the trial starts at a site.

Ethical considerations, information giving and written informed consent

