The primary analysis will compare all patients allocated to dexamethasone versus those allocated to placebo, on an 'modified intention-to-treat' basis. Modified intention-to-treat basis, which will include all patients who were randomly assigned, except those who withdrew consent, those who were lost the follow up or had protocol violations. Protocol violations corresponded to those patients who did not complete the 12-day treatment duration. A descriptive analysis of the baseline variables will be made for each treatment group, followed by a comparison between both groups.

In the secondary analysis a logistic regression model will be built to estimate the effect of dexamethasone and placebo on the patient's functional status measured with the GOSE at one month and at 6 months. The scale will be dichotomized in unfavorable outcome (GOSE 1-6) and favorable outcome (GOSE 7-8). In this analysis the primary outcome will be adjusted by age, pupil reactivity, blood pressure and GCS. To choose a model, the adequacy and goodness of fit will be measured.

Since the severity of the initial injury will significantly determine the final outcome of the patient, regardless of any treatment, the results of this study will be analyzed using the 'sliding dichotomy'. According to this analysis, patients with a less severe initial injury should have a better recovery than those with a severe initial injury. For example, a moderate disability in a patient for whom no more than death or severe disability could be expected is considered a good outcome, and vice versa, consider a moderate disability in a patient with excellent initial prognosis as poor outcome. Patients with a

severe initial injury (GCS score of 4 to 5 or, or with a GCS motor score of 2 to 3) will be considered to have a favorable outcome if the 6-month GOS-E score is 3 or higher. Patients with a moderate-to-severe initial injury (GCS score of 6 to 8 or, GCS motor score of 4 to 5) will be considered to have a favorable outcome if the 6-month GOS-E score is 5 or higher, and those with a less initial injury (GCS score of 9 to 12, GCS motor score of 6) will be considered to have a favorable outcome if the 6-month GOS-E score is 7 or higher.

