The purpose of the sliding dichotomy approach is to increase the sensitivity (to lower the false negative rate) of the analysis. All these variables will also be analyzed in a pre-specified subgroup analysis comparing patients with a pericontusional edema volume of more than 10 mL in the pre-inclusion computed tomography (CT) scan in the study with those who have less than 10 mL of edema volume in the same CT study.

Interim analysis

Since the data available in this type of patients receiving this treatment are scarce and inconclusive as to the primary outcome variable, we will perform an interim analysis. A statistician ([name]) will blindly perform an interim analysis calculating the conditional power, an approach that quantifies the probability of obtaining a significant result at the end of the study given the data available after one year enrolling patients.

Since the probability chosen for futility in this trial is very small (< 0,15), it can be concluded that it would be useless to continue the trial. This interim analysis will be performed at the end of the first year since the inception of the trial, when it is estimated that about 100 patients will have been recruited. At the same time, a safety analysis will be also performed, focused on the adverse effects collected during the first year.

The results will be assessed and discussed by an independent Data Monitoring Committee, formed by one statistician and two experts in TBI, who will inform and make recommendations to the Trial Steering Committee, which will finally make the decisions.

Follow-up

No extra tests are required for the trial but a case report form should be completed at the end of the 12- day treatment, or at death or hospital discharge if either happens sooner. The GOSE and the neuropsychological evaluations will be performed one month and 6 months after the TBI. Both evaluations will be performed by clinical

neuropsychologists, and the protocol used will always follow the same process. The neuropsychological tests that will be performed are described in the Supplemental data

Sponsorship and trial management

This research project has no sponsor. The trial will be coordinated by the Trial Steering Committee (TSC).

Indemnity

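### The primary comparison names no test and reads as unadjusted; adjustment for age, pupils, blood pressure and GCS is left to the secondary analysis, probably at some cost in power

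*Combined protocol and SAP*

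**What the plan says.** All of this is in the combined protocol and SAP.

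- **Primary comparison (Analysis).** "The primary analysis will compare all patients allocated to dexamethasone versus those allocated to placebo", on a modified intention-to-treat set. No test, effect measure or covariate is named here or elsewhere.
- **Adjusted model (Analysis).** A logistic regression for GOSE at one and six months, split at 7-8 versus 6 or less, is introduced as the secondary analysis. "In this analysis the primary outcome will be adjusted by age, pupil reactivity, blood pressure and GCS". Its form is left open: "To choose a model, the adequacy and goodness of fit will be measured".
- **Severity (Analysis).** The sliding dichotomy is justified by this premise: "Since the severity of the initial injury will significantly determine the final outcome of the patient, regardless of any treatment". Its aim is stated: "The purpose of the sliding dichotomy approach is to increase the sensitivity (to lower the false negative rate) of the analysis". Its cut-points are on the six-month scale; the middle severity group, for example, is "considered to have a favorable outcome if the 6-month GOS-E score is 5 or higher". It is not labelled primary or secondary.
- **Endpoint and size (Sample size and treatment effect size that should be detectable).** "The primary endpoint for the DEXCON TBI trial is the good recovery (GOSE 7-8) one month after the TBI". The target is 50% versus 62%, two-sided 5%, about 80% power, 600 patients including 10% inflation. The Primary outcome section and Supplemental data 1 name both one and six months.

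**The concern.** The plan says baseline severity largely drives outcome, wants to reduce false negatives, and already lists four prognostic covariates. It then does not attach them to the comparison that decides the trial. If they predict good recovery, a primary test that uses them detects the same 12-point effect more often with the same patients. If they predict weakly, almost nothing changes either way.

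The unnamed primary test is a fault on any reading, because two analysts could follow the text and report different primary p-values.

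**Working it through.** **1. Reproduce the plan's sample size.** Inputs from the sample size section: p0 = 0.50, p1 = 0.62, two-sided alpha 0.05, power 0.80, 10% inflation. Allocation is 1:1 (Randomization). The pooled two-proportion formula gives, per arm:

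n = [1.960·√(2·0.56·0.44) + 0.842·√(0.50·0.50 + 0.62·0.38)]² / 0.12² = (1.376 + 0.586)² / 0.0144 ≈ 267.4, so 268.

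The total is 536, and 536/0.9 = 596 against the stated 600. A continuity-corrected version gives 632 and a one-sided version 469; neither matches. The size fits an unadjusted two-proportion test, although such a formula could also have been used ahead of an adjusted analysis.

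**2. Power of the unadjusted test.** With 600·0.9 = 540 evaluable (270 per arm):

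(0.12 − 1.960·√(0.4928/270)) / √(0.4856/270) = 0.855, so power is 80.4%.

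The stated power holds.

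**3. What adjustment would add.** The documents give no AUC, R² or odds ratio for the covariates, so AUC is an assumed range. The simulation used 10,000 trials per row with 540 analysed and marginal rates held at 50% and 62%. Randomisation was in blocks of 2 within hospital. Other assumptions:

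- 2 sites of 60 and 42 of 10; hospital SD 0.5 on the logit scale
- age normal(52, 20) truncated to 18-85
- GCS 4-15 with 55% at 13-15; two-level pupils linked to GCS
- a quadratic blood pressure effect, fitted as linear
- no futility stop or analysis-set exclusions

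Monte Carlo error is about 0.4 points for power.

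| AUC | Unadjusted | Adjusted | Gain (points) | Variance ratio of risk difference |
|---|---|---|---|---|
| 0.50 | 81.0% | 80.6% | −0.4 | 0.99 |
| 0.55 | 81.3% | 81.3% | 0.0 | not computed |
| 0.60 | 81.2% | 82.1% | 0.9 | 0.96 |
| 0.65 | 81.5% | 83.7% | 2.2 | 0.92 |
| 0.70 | 81.2% | 85.5% | 4.3 | 0.87 |
| 0.74 | 81.0% | 88.1% | 7.1 | 0.82 |
| 0.78 | 80.5% | 89.9% | 9.4 | 0.76 |

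At AUC 0.70 the variance ratio to three places is 0.871. 540/0.871 = 620 evaluable, or 620/0.9 = 689 randomised, which is 89 more than 600. The formula in step 2 at 310 per arm gives 85.5%, in agreement with the simulation.

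**4. Robustness.**

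- Simulations with other covariate structures gave 80.4 v 82.3% (AUC 0.63), 81.1 v 85.7% (0.70), 80.6 v 86.0% (0.72), 80.3 v 87.9% (0.76) and 79.2 v 88.9% (0.79). One run at 0.75 gave a smaller gain, 82.0 v 87.5%.
- With hospital SD 0 and AUC 0.50, power was 81.4 v 80.8%, a loss of 0.6 points.
- With 20% unassessable GCS (pooled mean plus indicator) and 10% missing pupils and blood pressure, adjusted power at AUC 0.70 was 84.6%.
- Null rejection in the main simulation was 4.2-5.3% adjusted and 4.2-5.4% unadjusted.

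**5. Open model form.** At AUC 0.70, over 18 codings of the same covariates (4,000 null trials), size was 4.9% for a fixed form, 5.2% when chosen by AIC, and 6.8% for the most favourable coding.

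**The case against.** The strongest reply is that this concerns rank only. The same four-covariate model on the same outcome is already planned, the sliding dichotomy uses severity again, and no result is biased or lost. This does not dispose of the point, because the primary test decides the trial's conclusion and the sliding dichotomy is defined at six months with no stated rank.

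Several parts of the reply stand:

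- **Unadjusted is inferred.** A reader might take the plan to commit to an unadjusted test. It does not; it names no test.
- **The gain is not in the documents.** The sentence on severity introduces the six-month sliding dichotomy and does not say how well these four covariates predict GOSE 7-8 at one month. The exclusions (prior craniotomy, extracranial injury score above 18, GCS 3 with bilateral dilated pupils) may narrow the prognostic range. The figure of 89 patients belongs to one assumed AUC.
- **Choosing by fit did no visible harm.** A reader might infer that the goodness-of-fit step inflates type I error. The check does not show that: 5.2% against 4.9% is within simulation error. The 6.8% needs deliberate selection of the best coding, which the plan does not propose, and the statistical team is blinded.

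**Conclusion.** The point holds as a loss of efficiency, conditional on reading the primary comparison as unadjusted. A reader might go further and conclude that the primary test is invalid or the trial underpowered. The documents do not support that: the unadjusted test keeps its 5% level and has 80.4% power at 540 evaluable.

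The forgone power is about 0 points at AUC 0.50, 1 to 2 at 0.60-0.65, 4 to 5 at 0.70, and roughly 7 to 9 at 0.75-0.78. These figures assume exactly 10% loss, the 50% and 62% rates, and a prognostic strength that the documents do not give. The futility rule and the exclusion of withdrawals, losses and treatment non-completers are separate issues and are not part of this conclusion. The change should be made, because the possible gain is moderate and the worst-case loss very small.

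**What to change.** Amend the Analysis section with Trial Steering Committee agreement, as Protocol development requires. Do so before any comparative data are analysed: before the one-year interim or, if that has passed, before the main analysis is run. Unblinding would be too late a deadline, since Randomization keeps the codes concealed until after the main analysis.

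- **Primary model.** One logistic regression of GOSE 7-8 at the primary time point on treatment, age, GCS, pupil reactivity and one named blood pressure measure. First reconcile the one-month endpoint in the sample size section with the two time points in Primary outcome and Supplemental data 1, and state the rank of the sliding dichotomy.
- **Covariates.** Use values measured before randomisation. Supplemental data 1 times the baseline neurological scores 30 minutes before the first dose, which may fall after randomisation, so a pre-randomisation GCS should be confirmed. Fix the coding and the handling of unassessable GCS and other missing values in advance. Use goodness of fit only as a diagnostic.
- **Test and estimate.** Name the test of the treatment coefficient, for example the likelihood ratio test. Report the standardised risk difference with a 95% CI (delta method or bootstrap) beside the odds ratio.
- **Hospital.** Randomisation lists are by hospital, so decide in advance whether hospital enters the model and in what form.
- **Sensitivity and interim.** Keep the unadjusted two-proportion comparison as a sensitivity analysis, and base the interim conditional power on the same primary statistic.

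Cost: slightly more analysis work, no extra patients, and up to about 0.6 points of power if the covariates predict nothing. The odds ratio becomes conditional: 50% versus 62% is 1.63 without covariate effects but 1.91 at an assumed R² of 0.25. The risk difference beside it keeps the 12-point target readable.

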- Patients with inability to take medication orally due to swallowing problems in which it is not indicated to place a nasogastric tube.
- Pregnant or breastfeeding patients.
- Patients in a GCS 3 points situation with bilateral dilated pupils.
- Patients with associated spinal cord injuries.
- Patient with any systemic condition that contraindicates the use of corticosteroids.

Randomization

To ensure a balanced sample size across groups over time, the statistician of the study will apply the block randomisation method with a block size of 2 (two possible sequences: AB and BA) and will be generated with the statistical package R, version 3.5.3, a list for each hospital. A limited number of treatments will be available in each

hospital, sent from the Pharmacy Department of Son Espases Hospital, which will be numbered, and will be assigned in a correlative manner.

Patients, clinical staff, evaluators of the results as well as the statistical team will be blinded to the assignment of medications.

Only the pharmacist, who masks the capsules and labels the containers, will know the assignment of the codes, and will keep them blind until the last phase of the study, after the main statistical analysis, or when unmasking is required.

Once it is verified that the patient meets all the inclusion criteria and none of the exclusion criteria, and after signing the informed consent by the patient himself or by the closest relative, the doctor responsible for the patient will correlative assign the number to the patient.

Settings

Initially, the study will be carried out in Son Espases Hospital (Palma de Mallorca) and 12 de Octubre Hospital (Madrid). During the first year, all possible patients will be tried to be recruited. A minimum of 60 patients are expected between the two hospitals.

If after the first year interim analysis the Trial Steering Committee (TSC) decides to continue the trial, recruitment will begin in the hospitals included in the Spanish National Registry of Traumatic patients in the ICU (RETRAUCI Network) which includes 56 public hospitals.

Outcome measures

After a patient has been randomized, the outcome will be collected even if the trial treatment is interrupted or is not actually given

Primary outcome

The primary outcome is the functional status (outcome) of TBI patients one and six months after the trauma according to the Glasgow Scale Outcome Extended (GOSE).

Secondary outcomes (Supplemental data)

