The symptoms associated with TBI will be studied daily through the Rivermead Post Concussion Symptom (RPQ) scale. The RPQ is a questionnaire that measures the severity of symptoms associated with TBI. The questionnaire contains 16 symptoms and the patient is asked to quantify these symptoms during the past 24 hours.

In each case, the symptoms are compared with the severity of these symptoms before the trauma. The symptoms range from 0 to 4 points: 0: it has not presented such a symptom; 1: it has not been a bigger problem than before the TBI; 2: slight problem; 3: moderate problem; 4: serious problem.

The RPQ scale will be performed once daily during the 12 days of treatment.

-Compare the volume of pericontusional edema before and after 12 days of treatment in both groups of patients.

In each center, researchers will record the volume of the lesions including the hemorrhagic portion and the pericontusional edema using the ABC / 2 methodology. In the case of multiple contusions, each of them will be measured separately up to a number of 3, starting with the largest.

The image will be analyzed using a standard window for all cases (window level 60 and width of 100 UH), thus ensuring a similar gray scale in the different centers. A measurement of the largest diameter (A) will be made in each contusion, followed by the largest perpendicular diameter to A (B) and the number of cuts in which the contusion (hyperintense area and perilesional hypodense area) can be identified (C). The total volume of the bruises will be equal to the sum of the individual volumes of each one, whose volume results from multiplying the three diameters and dividing them by two. Once this process has been carried out, a measurement will only be made of the hyperdense portion of the contusions to establish the volume of the edema:

Edema volume = total volume-volume hyperdensity.

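### The secondary adjusted GOSE model leaves out baseline pericontusional edema volume, although the trial already measures it before randomisation: a minor, essentially free improvement

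*Combined protocol and SAP*

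**What the plan says.** The Analysis section describes the primary analysis as a comparison of the two arms on a modified intention-to-treat basis and names no covariates for it. It then introduces, as the secondary analysis, a logistic regression of dichotomised GOSE at one and six months: "In this analysis the primary outcome will be adjusted by age, pupil reactivity, blood pressure and GCS". The choice of these four covariates is not explained. The section adds that adequacy and goodness of fit will be used in choosing a model, without defining a procedure.

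The only pre-specified subgroup, at the end of the same section, compares patients with "pericontusional edema volume of more than 10 mL in the pre-inclusion computed tomography (CT) scan" with those below that threshold.

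The measurement is described in Supplemental data 1. At each centre, "researchers will record the volume of the lesions including the hemorrhagic portion and the pericontusional edema" by the ABC/2 method, for up to the three largest contusions. Edema volume is obtained by subtracting the hyperdense volume from the total volume. The images are read again centrally by a semi-automatic method. Figure 2 dates the inclusion CT to the 24 hours before randomisation, so this is a true baseline value.

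The Randomization section specifies a "block randomisation method with a block size of 2 (two possible sequences: AB and BA", with one list per hospital. Lesion and edema size are not strata.

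**The concern.** Edema is what the trial aims to treat. Visible pericontusional edema is an inclusion criterion, and its volume is the one baseline feature singled out for a subgroup. A reader would expect it in the adjusted model, and it is absent without explanation.

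If edema volume predicts recovery beyond age, pupils, blood pressure and GCS, leaving it out has two consequences. The adjusted test has somewhat less power than it could have. And if the arms happen to differ in edema volume, the adjusted estimate carries that difference. The 10 mL subgroup analysis does not fill the gap: it asks whether the treatment effect varies with edema size and does not adjust the overall effect.

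There is also a matter of order. The plan compares baseline variables between arms and gives no rule for what follows if edema differs. Adding volume at that stage would be a data-driven choice. Leaving it out would expose the adjusted result to challenge.

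**Working it through.** **The plan's own figure.** Inputs from the sample size section: 50% versus 62%, two-sided 5%, about 80% power, 10% inflation. With the pooled variance and mean rate 0.56:

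n per arm = [1.960 × √(2 × 0.56 × 0.44) + 0.842 × √(0.50 × 0.50 + 0.62 × 0.38)]² / 0.12² = 267.4, so 268 per arm and 536 in total. Then 536 / 0.9 = 596, which agrees with 600. The calculation is unadjusted, so the adjusted model's covariates do not enter it. Patients analysed after 10% loss: 600 × 0.9 = 540.

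**Assumptions not in the documents.** The four listed covariates are represented by one score with SD 1 logit. Edema volume is standardised, with an effect of 0.3, 0.5 or 0.8 logits per SD, and is independent of that score. The treatment effect is set to give 50% versus 62% overall.

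**Power of the adjusted Wald test** (540 patients, 4,000 simulated trials per row):

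| Effect of volume (logits per SD) | Four covariates | Plus volume | Gain (points) |
|---|---|---|---|
| 0 | 0.870 | 0.870 | 0 |
| 0.3 | 0.863 | 0.869 | 0.6 |
| 0.5 | 0.867 | 0.880 | 1.3 |
| 0.8 | 0.859 | 0.894 | 3.5 |

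A separate simulation (3,000 trials per setting) expressed the effect as an odds ratio per SD and let volume correlate with the score at 0 or -0.3. The gains, in points, for correlation 0 and -0.3 were:
- odds ratio 1.25: 0.6 and 0.7
- odds ratio 1.5: 1.2 and 0.9
- odds ratio 2.0: 2.8 and 2.4
- odds ratio 2.5: 5.6 and 4.2

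Type I error in the two adjusted models was 4.6% to 5.4%, with or without volume.

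**Where the gain comes from.** At an odds ratio of 1.5 per SD and correlation 0, adding volume moves the treatment log odds ratio from 0.591 to 0.613 and its standard error from 0.193 to 0.197. At 2.0 the log odds ratio goes from 0.581 to 0.640 and the standard error from 0.191 to 0.201. The standard error rises. Power improves because the conditional log odds ratio grows by more.

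**Chance imbalance.** The difference between arms in a standardised baseline variable has standard error √(4/540) = 0.086. Two standard errors are 0.172 SD. The resulting shift in the difference in GOSE 7-8 is approximately 0.172 × effect per SD × average p(1 - p). The last term must be averaged over the assumed covariate spread and the two arms. Taking it at the mean rate (0.56 × 0.44 = 0.246) would overstate the shift.

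| Effect (logits per SD) | Average p(1 - p) | Shift (points) | Share of 12 points |
|---|---|---|---|
| 0.3 | 0.199 | 0.172 × 0.3 × 0.199 = 1.0 | 9% |
| 0.5 | 0.194 | 0.172 × 0.5 × 0.194 = 1.7 | 14% |
| 0.8 | 0.185 | 0.172 × 0.8 × 0.185 = 2.5 | 21% |

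An imbalance this large arises in roughly 1 trial in 20. The average absolute shift is √(2/π) × 0.086 × effect × average p(1 - p), or 0.4, 0.7 and 1.0 points. With about 100 patients, the number the Interim analysis section expects after the first year, two standard errors are 2 × √(4/100) = 0.4 SD, and the shift runs from 2.4 to 5.9 points.

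**The case against.** The strongest case against is that nothing here is an error. The model is secondary, the plan already adjusts for four baseline prognostic variables and adds a severity-based sliding dichotomy, and which further covariate to include is a matter of judgement. The documents give no prognostic strength for edema volume. The background argues that vasogenic edema may respond to steroids, and the subgroup concerns effect modification. Neither shows that volume predicts recovery. All of this stands, and it is why the point is minor. It does not defeat the suggestion, because the value is already collected and including it is harmless if it turns out not to be prognostic.

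The measurement objection stands in part. Edema volume is a component of total volume, so the two should not be entered together. Site readings cover at most three contusions, and their agreement with the central method has yet to be established. This argues for one named reading, not for omission.

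A reader might infer more than the documents support:
- That the trial's main result is compromised. It is not: the primary comparison states no covariates.
- That precision is lost. In a logistic model, adding volume increases the standard error of the log odds ratio. What may be lost is some power.
- That chance imbalance biases the test. Under randomisation it is already reflected in the error rate.
- That contusion volume has the same standing. Only edema volume defines the subgroup.

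The modified intention-to-treat set excludes patients who did not complete 12 days of treatment. That could unbalance the arms for other reasons, but it is a separate matter that covariate adjustment would not cure.

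**Conclusion.** The omission is real but minor. It affects only the secondary adjusted model at one and six months. If edema volume carries 0.3 to 0.5 logits per SD beyond the listed covariates, the adjusted test gains about 1 point of power, and at 0.8 it gains 3 to 4. Over the same range, adjustment corrects for a two-standard-error imbalance worth 1.0 to 2.5 percentage points with 540 analysed. These sizes rest on the assumed prognostic strength and on the SD of 1 logit for the other covariates. Neither figure is in the documents. If volume is not prognostic, the gain is zero and so is the loss.

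**What to change.** In the Analysis section, add baseline pericontusional edema volume from the inclusion CT to the covariates of both the one-month and the six-month GOSE models. Enter it as a single pre-specified continuous variable, log-transformed. Name the central reading as the source, and allow the site ABC/2 reading only where the central one is missing. Do not enter total contusion volume beside it, because edema volume is total minus hyperdense volume. If hemorrhagic burden is also wanted, use the hyperdense volume. If the trial team prefers to leave edema volume out, one sentence giving the reason would suffice.

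The cost is a short addition to the text and one parameter in a model with about 540 patients. No new measurement is needed, and the sample size and primary analysis do not change. The fallback does mix two reading methods, so the number of patients on the site reading should be reported.

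### The futility rule (conditional power below 0.15 at one year) names neither the assumed effect nor the direction, and the stated 80% power makes no allowance for the look

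*Combined protocol and SAP*

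**What the plan says.** The Interim analysis section says a statistician "will blindly perform an interim analysis calculating the conditional power", defined as "the probability of obtaining a significant result at the end of the study given the data available after one year enrolling patients". The criterion is "the probability chosen for futility in this trial is very small (< 0,15), it can be concluded that it would be useless" to continue. The look falls at the end of the first year, "when it is estimated that about 100 patients will have been recruited". The Settings section gives a lower figure: "A minimum of 60 patients are expected between the two hospitals". The DMC recommends to the Trial Steering Committee (TSC), "which will finally make the decisions", and the section End of trial for participants likewise leaves the final decision to the TSC.

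On power, the sample size section says "A study with 600 patients would have about 80% power (two sided alpha=5%) to detect a 12% absolute increased (from 50% to 62"; the outcome meant is GOSE 7–8. The primary endpoint there is at one month, and the only inflation named is 10% for non-adherence. The same section announces the interim futility analysis.

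On blinding, the Randomization section says only the pharmacist knows the codes, which stay blind until "after the main statistical analysis, or when unmasking is required". The Interim analysis and DMC sections describe the statistician's work as blind, and the safety section has the DMC review adverse events blinded.

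**The concern.** Conditional power has no single value until two things are fixed: the effect assumed for the remaining patients, and which final results count as significant. The plan fixes neither, and the futility sentence is not written as a condition. Two competent statisticians could therefore give the DMC opposite advice from the same data.

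The look carries weight. It decides whether recruitment extends from two hospitals to the RETRAUCI network of 56, and the Financial support section secures funding for up to 100 patients only. A rule that often stops an effective treatment lowers the trial's power. A rule that almost never triggers does not do the job of a futility look. The present text admits both.

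**Working it through.** **Inputs.** Sample size section: 50% v 62%, two-sided alpha 5%, 600 patients, 10% inflation. Randomization section: blocks of two, so 1:1. Interim analysis section: threshold 0.15 and about 100 patients. Settings section: minimum 60. Assumptions made here: 540–600 evaluable at the end, and the rule followed whenever it is met.

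**1. The plan's own figure.** Pooled two-proportion formula, per arm:

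n = [1.96·√(2·0.56·0.44) + 0.8416·√(0.50·0.50 + 0.62·0.38)]² / 0.12² = 267.4, so 268 per arm, 536 in all.

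536/0.9 = 596 and 536 × 1.1 = 590. The stated 600 is reproduced as a single-stage size, so nothing is left over for the look.

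**2. Current-trend rule.** With information fraction t = n₁/N and interim statistic Z, conditional power in favour of dexamethasone is

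CP = Φ[(Z/√t − 1.96)/√(1−t)].

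CP < 0.15 is equivalent to Z < √t·[1.96 − 1.036·√(1−t)]. At 100 of 600 (t = 0.167) the boundary is Z < 0.414; at 100 of 540 (t = 0.185) it is Z < 0.441. Multiplying by √(2·0.56·0.44/50) = 0.0993 gives observed differences of about 4.1 and 4.4 percentage points. If the arms are unlabelled and either direction counts, the term Φ[(−Z/√t − 1.96)/√(1−t)] is added to CP.

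**3. Design-effect rule.** CP = Φ[(Z√t + θ(1−t) − 1.96)/√(1−t)], with θ = 0.12/√[(0.25 + 0.2356)/n]. This is 2.983 at 300 per arm and 2.830 at 270. At 100 patients, CP < 0.15 needs Z below about −3.6 (of 600) or −3.0 (of 540).

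**4. Results by exact binomial enumeration, true rates 50% v 62%.** Power is the probability of continuing and then having final Z > 1.96. With no look it is 85.0% (300 per arm) and 80.6% (270 per arm).

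| Per arm: look / final | Trend, direction known: stop / power | Trend, unlabelled two-sided: stop / power |
|---|---|---|
| 50 / 300 | 23.3% / 68.5% | 18.9% / 71.1% |
| 50 / 270 | 23.8% / 65.7% | 19.5% / 67.7% |
| 30 / 300 | 29.0% / 63.1% | 19.9% / 69.4% |
| 30 / 270 | 29.0% / 60.7% | 19.9% / 66.2% |
| 45 / 270 (10% missing at both times) | 20.2% / 68.1% | 13.1% / 71.8% |
| 27 / 270 (10% missing at both times) | 31.4% / 58.7% | 21.8% / 64.6% |

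Under the design-effect reading with 50 per arm at the look, stopping is about 0% and power stays at 81–85%.

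**5. Stopping under other truths, 50 per arm, exact.** With no effect (50% v 50%), the direction-known trend rule stops 69%, the unlabelled two-sided rule 38%, and the design-effect rule 0.02–0.2%. With a 12-point harm (50% v 38%), the direction-known trend rule stops 96%. The unlabelled rule stops 19–20%, the same as for a 12-point benefit, because it cannot tell them apart.

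**6. A further reading.** If no effect is assumed for the remaining patients, the normal formula gives power of only about 1–12%. Nothing in the text points to this reading, but nothing excludes it.

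**The case against.** The strongest reply is that the power loss belongs to a reading the plan never adopts. Conditional power on any assumption is calculated from the data so far, so the plan's definition does not select the current trend, and under the design effect nothing is lost. The rule is also advisory: the DMC recommends, the TSC decides, and the TSC also weighs recruitment and overall event rates. A demanding gate before expansion may be deliberate. All of this stands, so the figures describe a rule that is followed, not the trial's actual power. It does not remove the omission, since an advisory rule must still be computable.

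Several stronger readings are tempting but not supported:

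- *That the trial has only 61–69% power.* This needs the current trend, a look at 60 patients and mechanical adherence. The documents commit to none of these.
- *That the direction-known figures are the ones that apply.* The blinding statements fit unlabelled arms at least as well, and there the loss is smaller.
- *That the plan leaves patients unprotected from harm because an unlabelled rule stops few harmful trials.* Futility is not the harm safeguard. The plan has a safety analysis at the same look, DMC safety oversight, and a separate standard of proof under Standard operating procedures.
- *That the codes must be released for the look.* Direction has to be available to this calculation, but the documents do not dictate how. The Randomization section's provision for unmasking may mean only the individual emergency unblinding described under Unblinding.
- *That the rule stops unless dexamethasone leads by three patients at 50 per arm.* This depends on the event rates: 34 v 32 of 50 gives Z = 0.422, above the 0.414 boundary for 600.

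Futility stopping alone does not inflate the type I error, and no such claim is made.

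**Conclusion.** The concern holds as an unspecified rule together with a power statement that ignores it. On either current-trend reading, if the rule is followed and the planned effect is true, exact power falls from 81–85% to about 66–71% with 100 patients at the look and 61–69% with 60. It is 59–65% if 10% are also missing at a 60-patient look. On the design-effect reading power is intact, but the rule stops at most about 0.2% of no-effect trials at 100 patients. Either the stated 80% is not delivered or the look has almost no futility function, and the text does not say which.

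The omission itself is certain. The size depends on the reading chosen, on 540–600 evaluable patients, and on adherence to advisory guidance. This should be fixed, and it can be fixed without changing the threshold or the maximum enrolment.

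**What to change.** 1. **Interim analysis:** write the rule as a condition. For example: futility is recommended if conditional power is below 0.15, where conditional power is the probability of a significant final result in favour of dexamethasone on one-month GOSE 7–8, assuming [the current trend / 50% v 62%] for the remaining patients. The choice in brackets is the investigators'.
2. **Sample size section:** if the current-trend rule is kept, restate power with the look included, and note that the rule is advisory.
3. **Randomization, Safety and Adverse events, Interim analysis, and DMC sections:** say consistently how direction is known for this calculation while the trial team stays blinded.
4. **Operating characteristics:** report the stopping probabilities under the planned effect, no effect and harm, at the number of patients expected to have a one-month GOSE at the look.

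These are wording changes plus a short calculation. The downside is a less favourable stated power if the current-trend rule is kept.
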